6.1.2 Post Baseline Period

On-treatment AEs will be defined as AEs with an onset date-time on or after the date-time of the first dose of study treatment (or with an onset date on or after the day of first dose of study treatment if time is not collected or is missing). An AE will be counted as on-treatment if the event occurred within 100 days of the last dose of study treatment.

On-treatment evaluations (laboratory tests, pulse oximetry and vital signs) will be defined as evaluations taken after the day (and time, if collected and not missing) of first dose of study treatment. An evaluation will be counted as on-treatment if it occurred within 100 days of the last dose of study.

6.2 Treatment Regimens

For each of the 5 cohorts, subjects in module A will receive nivolumab 3 mg/kg every 2 weeks; subjects in Module B will receive nivolumab 3 mg/kg plus ipilimumab 1 mg/kg, every 3 weeks for 4 doses followed by nivolumab 3 mg/kg every 2 weeks.

6.3 Populations for Analyses

Population	Description
Enrolled	All participants who sign informed consent. This is the dataset for disposition.
Treated	All enrolled participants who received at least one dose of study drug. This is the dataset for safety evaluation.
Safety Lead-in participants	In Module A, the first 14 DLT-evaluable participants in Cohort 1 and the first 10 DLT-evaluable participants in Cohorts 2-5; in Module B, the first 10 DLT-evaluable participants.
Response-evaluable participants	All treated participants with measurable disease at a baseline tumor assessment (Source: CRF).

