5.1.2 Safety Lead-in

A safety lead-in will be implemented because nivolumab, as monotherapy or immediately after RT or in combination with ipilimumab, has not been studied in pediatric participants with CNS tumors.

In Module A, 6 participants with newly-diagnosed DIPG (Cohort 1) will be evaluated for safety of nivolumab administered following RT and 10 participants with recurrent CNS tumors will be evaluated for safety of nivolumab monotherapy. Tolerability and safety of the treatment will be determined after these participants have completed 3 doses and a minimum of 6 weeks on study or discontinued due to dose-limiting toxicity (DLT; see [Section 5.1.3](#)). Safety evaluation will be conducted based on criteria described in [Sections 9.2](#) and [9.4](#). Enrollment will proceed to expansion for Module A only if not more than 2 DLTs are observed in Cohort 1, and separately only if not more than 3 DLTs are observed among the 10 participants in Cohorts 2-5. If no DLTs are observed in the first 5 (of 6) participants in Cohort 1 or in the first 8 (of 10) participants in Cohorts 2-5, then after review by the SSC, enrollment to corresponding Expansion phase may proceed. Participants who discontinue study treatment prior to 3 doses for reasons other than drug-related toxicities are not evaluable for DLT and will be replaced.

If exactly 2 DLTs are observed in Cohort 1 or exactly 3 DLTs are observed in Cohorts 2-5, the SSC will make a determination as to continuation of enrollment based on the nature, severity, and reversibility of the AEs observed. In this circumstance, enrollment will be stopped until the DMC has agreed.

In Module B, 10 participants from any Cohort (ie, those for which Module A has closed) will be evaluated for safety of nivolumab in combination with ipilimumab. Tolerability and safety of the treatment will be determined after these participants have completed 2 doses and observed for a minimum of 6 weeks or discontinued due to DLT. Safety evaluation will be conducted based on criteria described in Sections 9.2 and 9.4. If not more than 3 DLTs are observed among the 10 participants in Cohorts 1-5, enrollment will proceed into expansion for Module B. Participants who are not evaluable for DLT will be replaced. The same condition as noted above will be implemented if exactly 3 DLTs are observed in this safety population.

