10.2 Populations for Analyses

For purposes of analysis, the following populations are defined:

Population	Description
Enrolled	All participants who sign informed consent. This is the dataset for disposition.
Treated	All enrolled participants who received at least one dose of study drug. This is the dataset for safety evaluation.
Safety Lead-in participants	In Module A, the first 6 DLT-evaluable participants in Cohort 1 and the first 10 DLT-evaluable participants in Cohorts 2-5; in Module B, the first 10 DLT-evaluable participants.
Response-evaluable participants	All treated participants with measurable disease at a baseline tumor assessment (Source: CRF).
[REDACTED]	[REDACTED]
[REDACTED]	[REDACTED]

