10.3.2 Safety Analyses

All safety analyses will be performed on the treated population.

Endpoint	Statistical Analysis Methods

Primary
 
Module A and B Safety Lead-in:
 
Incidence of AEs, SAEs, drug-related AEs, AEs leading to discontinuation, and death.
 
AEs will be graded according to CTCAE v4.03.
 
Incidence of laboratory abnormalities
 
Laboratory values will be graded according to CTCAE v4.03.
	
Module A and B Safety Lead-in:
 
Frequency distribution of treated participants with AE using the worst CTC grade. Participants will only be counted (1) once at the preferred term (PT) level, (2) once at the system organ class (SOC) level, and (3) once in the ‘Total participant’ row at their worst CTC grade, regardless of SOC or PT. By Cohort.
 
Lab shift table using the worst CTC grade per participant by Cohort.

Endpoint	Statistical Analysis Methods

Secondary
 
All Cohorts A1-A5, B1-B5:
 
Incidence of AEs, SAEs, drug-related AEs, AEs leading to discontinuation, and death.
 
AEs will be graded according to CTCAE v4.03.
 
Incidence of laboratory abnormalities
 
Laboratory values will be graded according to CTCAE v4.03.
	
All Cohorts A1-A5, B1-B5:
 
Frequency distribution of treated participants with AE using the worst CTC grade. Participants will only be counted (1) once at the preferred term (PT) level, (2) once at the system organ class (SOC) level, and (3) once in the 'Total participant' row at their worst CTC grade, regardless of SOC or PT. By Cohort.
 
Lab shift table using the worst CTC grade per participant by Cohort.

[REDACTED]	[REDACTED]

[REDACTED]

[REDACTED]

[REDACTED]

[REDACTED]

[REDACTED]

[REDACTED]

[REDACTED]

[REDACTED]

[REDACTED]

[REDACTED]

[REDACTED]

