2 STUDY DESCRIPTION

2.1 Study Design

This is an open-label, sequential-arm Phase 1b/2 clinical trial of nivolumab monotherapy and of nivolumab plus ipilimumab in pediatric participants with high-grade primary CNS malignancies.

This study includes 5 cohorts and 2 modules as described below:

Cohorts are defined by tumor type (histology):

Cohort 1: N = 22 participants with newly-diagnosed DIPG, including midline glioma with H3K27M mutation

Cohort 2: N = 15 participants with recurrent or progressive non-brainstem HGG, regardless of mutation status, including glioblastoma

Cohort 3: N = 15 participants with relapsed or resistant medulloblastoma

Cohort 4: N = 10 participants with relapsed or resistant ependymoma

Cohort 5: N = 18 participants with other recurrent subtypes of high-grade CNS malignancy (eg, pineoblastoma, AT/RT, germ cell tumor, and others)

The above intended target numbers for each Module are approximate.

Molecular phenotype analyses will be performed according to institutional standard. Details on the molecular subtype of the individual tumors will be reported when they become available.

Treatments are defined by Module:

Module A: nivolumab 3 mg/kg every 2 weeks, as monotherapy, and

Module B: nivolumab 3 mg/kg plus ipilimumab 1 mg/kg, every 3 weeks for 4 doses followed by nivolumab 3 mg/kg every 2 weeks.

Enrollment to Module A will open in parallel for all cohorts. The first 6 participants in Cohort 1 who are treated and DLT evaluable will be evaluated for safety before additional participants are treated in that Cohort. Separately, the first 10 participants treated and DLT evaluable in the recurrent disease Cohorts 2-5 (combined) will be evaluated for safety before additional participants are treated (see Schema in [Figure 2.1-1](#)) in those Cohorts. At regularly-scheduled teleconferences, the Study Steering Committee (SSC) will review safety, assess potential DLTs, and make recommendations regarding reopening of enrollment. See additional details in [Section 2.6](#).

[figure not shown]
Based on determination of adequate safety, enrollment will re-open for evaluation of efficacy to complete the planned number of participants for each cohort in Module A expansion. Participants evaluated in the safety lead-in will be included for evaluation of efficacy (i.e., the 6 participants with DIPG evaluated for safety in Cohort 1 are included in the 22 planned participants).

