4 ENDPOINTS

4.1 Primary

4.1.1 Safety lead-in Phase

The primary objective of safety lead-in will be assessed by the incidence of DLTs, SAEs, and AEs leading to discontinuation.

A dose-limiting toxicity (DLT) is defined as a drug-related AE occurring in the first 6 weeks of study treatment. A participant will be considered evaluable for a DLT if study treatment was delayed > 2 weeks or was discontinued due to a related AE, or if planned study treatment (3 doses of nivolumab in Module A, 2 doses of nivolumab plus ipilimumab in Module B) was administered and safety evaluation after 6 weeks on study is available to the SSC. Participants who discontinue treatment for a reason other than toxicity (i.e., without DLT) are not evaluable for DLT and will be replaced in enrollment.

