7.6 Safety

Primary safety analyses will be performed for safety lead-in participants which includes 3 groups: in Module A, the first 14 DLT-evaluable participants in Cohort 1, and the first 10 DLT-evaluable participants in Cohorts 2-5; in Module B, the first 10 DLT-evaluable participants.

Secondary safety analyses will be performed for all treated subjects and summarized by cohort and treatment.

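### The SAP sets the Module A Cohort 1 safety lead-in population at 14 DLT-evaluable participants; the protocol and the SAP's own design section say 6

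*SAP*

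**What the plan says.** The SAP gives two sizes for the Cohort 1 lead-in group in Module A.

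- SAP 6.3, in the row for safety lead-in participants: "In Module A, the first 14 DLT-evaluable participants in Cohort 1".
- SAP 7.6, naming the groups for the primary safety analyses: "in Module A, the first 14 DLT-evaluable participants in Cohort 1".
- SAP 2.1, describing the design: "The first 6 participants in Cohort 1 who are treated and DLT evaluable will be evaluated for safety".

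The protocol gives only 6.

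- Protocol 10.2, in the matching row of its population table: "In Module A, the first 6 DLT-evaluable participants in Cohort 1".
- Protocol 5.1.2: "6 participants with newly-diagnosed DIPG (Cohort 1) will be evaluated for safety of nivolumab administered following RT". The synopsis and protocol 5.1 agree.

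SAP 4.1.1 states what is measured: "The primary objective of safety lead-in will be assessed by the incidence of DLTs, SAEs, and AEs leading to discontinuation".

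On the population for safety analyses, protocol 10.3.2 states "All safety analyses will be performed on the treated population" and lists the lead-in as the primary safety analysis. SAP 7.6 instead bases the primary analysis on the DLT-evaluable lead-in set and keeps all treated subjects for the secondary analysis.

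**The concern.** The lead-in population is the denominator of a primary endpoint. A programmer working from SAP 6.3 and 7.6 would take the first 14 evaluable Cohort 1 participants. By design, the cohort pauses after the first 6 so that their safety can be reviewed before others are treated. A set of 14 therefore combines the lead-in participants with 8 who belong to the expansion, under the lead-in label. Both the incidence estimate and its apparent precision would change.

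Cohort 1 is also the group for which protocol 5.1.3 gives specific reasons for separate DLT assessment: the tumor's location and the short interval after radiotherapy. A blurred denominator is least welcome there.

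**Working it through.** **1. Is 14 derived from anything?** It is a definitional count with no power or alpha calculation behind it, so there is nothing to reproduce. The check is to compare every statement of the count.

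| Place | Cohort 1, Module A | Cohorts 2-5, Module A | Module B |
|---|---|---|---|
| Protocol synopsis, 5.1, 5.1.2 | 6 | 10 | 10 |
| Protocol 10.2 (population table) | 6 | 10 | 10 |
| SAP 2.1 (design) | 6 | 10 | 10 |
| SAP 6.3 (population table) | **14** | 10 | 10 |
| SAP 7.6 (primary safety analysis) | **14** | 10 | 10 |

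Only the Cohort 1 count differs. The lead-in total is 6 + 10 + 10 = 26 under the protocol and 14 + 10 + 10 = 34 under SAP 6.3.

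**2. Could a change of version explain it?** SAP 2.1 says 6, so the SAP disagrees with itself whichever protocol version it follows. The SAP's document history for version 2.0 lists no change to this population. Both Cohort 1 rules in protocol 5.1.2 (not more than 2 DLTs; early opening after none in the first 5 of 6) are written for a group of 6.

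**3. Effect on the denominator.** 14/6 = 2.33. Of the 22 planned Cohort 1 participants, 6/22 = 27% is the protocol's lead-in and 14/22 = 64% is the SAP's.

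**4. Effect on the reported incidence.** The DLT counts below are assumptions chosen for illustration. Intervals are 95% Clopper-Pearson, the method SAP 7.1 names for proportions: the lower limit is the 0.025 quantile of Beta(x, n − x + 1), and the upper limit is the 0.975 quantile of Beta(x + 1, n − x). When x = 0 the upper limit reduces to 1 − 0.025^(1/n).

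| DLTs in the first 6, none in the extra 8 | Reported on 6 | Reported on 14 |
|---|---|---|
| 0 | 0%, upper limit 1 − 0.025^(1/6) = 45.9% | 0%, upper limit 1 − 0.025^(1/14) = 23.2% |
| 1 | 16.7% (0.4% to 64.1%) | 7.1% (0.2% to 33.9%) |
| 2 | 33.3% (4.3% to 77.7%) | 14.3% (1.8% to 42.8%) |

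The sets are nested, so the result on 14 also depends on the extra 8. With 2 DLTs in the first 6 and k in the next 8, the reported figure is (2 + k)/14. It runs from 2/14 = 14.3% at k = 0 to 10/14 = 71.4% at k = 8. The upper end is an arithmetic limit, not an expected outcome.

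**5. The related mismatch.** A lead-in participant who was treated but replaced as not DLT-evaluable belongs to the treated population of protocol 10.3.2, but not to the set in SAP 7.6. The two texts can therefore give different lead-in summaries even after 14 becomes 6.

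**The case against.** The main counter-argument concerns consequence. The steering committee makes the expansion decision on 6. All Cohort 1 safety data appear in the planned secondary analysis of treated subjects. The lead-in objective is estimation, with no test or threshold attached to this population, and no efficacy result depends on it. If exactly 2 of the first 6 had a DLT, protocol 5.1.2 already sends the matter to the steering committee and the DMC, so a later table showing 2/14 would not mislead those decision-makers. All of this is correct and limits the point to reporting. It does not remove it, because the result reported on the wrong set is a primary endpoint.

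No legible text plans a confidence interval for DLT incidence, and the adverse-event displays are deferred to a core safety SAP that is not available here. The intervals above are therefore illustrative. The change in denominator and point estimate does not depend on them.

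SAP 2.1 and protocol 5.1 describe an enrollment pause rather than an analysis set, so they support 6 only indirectly. The direct conflict is protocol 10.2 against SAP 6.3 and 7.6. Because 14 appears twice, the documents cannot show whether it is a slip or a decision. The fix has to allow for both.

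Finally, protocol 10.3.2 can be read as meaning treated participants within the lead-in. That reading is fair and makes this the lesser part of the point. It still leaves treated participants who are not DLT-evaluable counted under one text and not under the other.

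**Conclusion.** The inconsistency is real and should be corrected before the lead-in analysis is reported. SAP 6.3 and 7.6 specify a primary safety population that the protocol does not define and SAP 2.1 contradicts. The size that follows from the documents alone is 14 participants against 6, a 2.3-fold denominator that includes 8 participants from outside the protocol's lead-in. The percentages shown rest on assumed DLT counts and indicate how far the reported incidence could move. What changes is the reported primary lead-in safety result in Cohort 1 of Module A. The expansion decision, the other two lead-in groups, the all-treated safety summaries and the efficacy analyses do not change.

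**What to change.** - In SAP 6.3 and SAP 7.6, change 14 to 6 for Cohort 1 in Module A, to agree with protocol 10.2 and SAP 2.1. Later Cohort 1 participants are then covered by the planned secondary analysis of all treated subjects.
- If 14 was intended, state the reason in the SAP, align protocol 10.2 and the design sections, and report the first 6 separately so that the result behind the expansion decision stays visible.
- In either case, add one sentence naming the set that carries the primary lead-in summary, so that SAP 7.6 and protocol 10.3.2 agree. It should say how treated lead-in participants who are not DLT-evaluable are handled.

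If 6 is right, the cost is two numbers and one sentence. No new data are needed and the sample size does not change. If 14 is right, the cost also includes a justification, a protocol alignment and a separate summary of the first 6.

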7 STATISTICAL ANALYSES

7.1 General Methods

Unless otherwise noted, the titles in the following subsections describe tabulations of discrete variables, by the frequency and proportion of subjects falling into each category, grouped by cohort and treatment (module). Percentages given in these tables will be rounded and, therefore, may not always sum to 100%. Continuous variables will be summarized by treatment group (with total) using the mean, standard deviation, median, minimum and maximum values. If a missing category is not being presented in the data display, only those subjects with non-missing values for the parameter being assessed are included in the percentage calculation.

Time to event distributions (i.e. progression free survival, overall survival [REDACTED] [REDACTED]) will be estimated using Kaplan Meier techniques. When appropriate, the median along with the corresponding log-log transformed 95% CI will be estimated. Rates at fixed timepoints (e.g. OS at 12 months) will be derived from the Kaplan Meier estimate along with their corresponding log-log transformed 95% confidence intervals¹⁰. Confidence intervals for binomial proportions will be derived using the Clopper-Pearson method¹¹.

7.2 Study Conduct

7.2.1 Accrual

The accrual pattern will be summarized per country, investigational site, and per month for all enrolled and treated subjects by cohorts and treatments. First dosing date, country, investigational site will be presented in a by subject listing of accrual for each cohort and treatment.

7.2.2 Relevant Protocol Deviations

The following programmable deviations will be considered as relevant protocol deviations and summarized by cohort and treatment group. Non-programmable relevant eligibility and on-treatment protocol deviations, as well as significant (both programmable and non-programmable) eligibility and on-treatment protocol deviations will be reported through [REDACTED] listings.

At Entrance:

- Subjects at age ≥ 22 or < 6 months
- Subjects have not received standard of care
- without previous first line treatment with at least radiotherapy and temozolomide (for Cohorts 1a and 1b only)
- Subjects with prior treatment of an anti-PD-1, anti PD-L1 and L2, or anti-CTLA-4 antibody, or any other antibody or drug specifically targeting T-cell co stimulation or checkpoint pathway
- Subjects without LPS (for subjects ≤ 16 years old) or Karnofsky(for subjects > 16 years old) performance status of 60 or higher
- Subjects with tumor size > 6 cm.
- Steroid (Dexamethasone or equivalent) use > 0.05 mg/kg/day

On-study:

- Subjects receiving anti-cancer therapy (chemotherapy, hormonal therapy, immunotherapy, standard or investigational agents for treatment of cancer) other than study therapy while on study therapy.
- Subjects treated differently than as assigned (subjects who received the wrong treatment, excluding the never treated).
- Steroid (Dexamethasone or equivalent) use > 0.05 mg/kg

Listings will also be provided.

7.3 Study Population

Unless otherwise specified, the following analyses will be presented by cohort and treatment group as “treated”

7.3.1 Subject Disposition

The total number of subjects enrolled (treated or not treated) will be presented by cohort along with the reason for not being treated.

Number of subjects who discontinued study treatment along with corresponding reason will be tabulated by cohort and treatment group as treated. Reason for discontinuation will be derived from subject status CRF page.

A subject listing for all treated subjects will be provided showing the subject’s first and last dosing date, off study date and reason for going off-study. A subject listing for subjects not treated will also be provided, showing the subject’s race, gender, age, consent date and reason for not being treated.

7.3.2 Demographics and Baseline Characteristics

The following baseline characteristics will be summarized by cohort and treatment group. All baseline presentations will identify subjects with missing measurements. Listings will also be provided.

- Age (descriptive statistics)
- Age category I (<18, ≥18)
- Age category II (<2, 2- <12, 12-<18, ≥ 18)
- Gender (male, female)
- Race (white, black, asian, other)
- Ethnicity (hispanic or non-hispanic, for US subjects only)
- Region (US/Canada, Europe, Rest of the World)
- Presence of a measurable lesion at baseline (Yes, No)
- Baseline performance status
- Height and Weight (descriptive statistics)
- Steroid Use (Yes, No)
- Time from Initial Disease Diagnosis to first dose date (<6 months, 6-<12 months, 12-<18 months, 18-<24 months, ≥24 months)
- All lesions (Investigator Tumor Assessments at Baseline): sites of disease, number of disease sites per subject.
- Target lesions (Investigator Tumor Assessments at Baseline): Presence of target lesions, site of target lesion, sum of longest diameter of target lesion.

7.3.3 Medical History

General medical history will be listed by subject.

7.3.4 Prior Therapy

The following will be summarized by cohort and treatment group.

- Prior systemic cancer therapy (yes/no)
- Prior agent received (generic name)
- Prior surgery related to cancer (yes/no)
- Prior radiotherapy (yes/no)

Agents and medication will be reported using the generic name. A listing by subject will also be provided including prior/current non study medication.

7.3.5 Baseline Examinations

Subjects with abnormal baseline physical exam results will be tabulated by examination criteria (eg neck, cardiovascular, lungs, etc), by cohort and by treatment group.

7.3.6 Discrepancies Between IVRS and CRF Cohorts

Summary tables (cross-tabulations) by treatment group for cohorts will be provided to show any discrepancies between what was reported through IVRS vs. CRF data (baseline).

7.4 Extent of Exposure

Listings will include all available exposure data. Analyses will be performed by cohort and treatment group “as treated” in all treated subjects, unless otherwise specified.

7.4.1 Administration of Study Therapy

The following parameters will be summarized (descriptive statistics) by cohort, study therapy (nivolumab and ipilimumab) and treatment group:

- Number of doses received
- Cumulative dose
- Relative dose intensity (%) using the following categories: < 50%; 50 - < 70%; 70 - < 90%; 90 - < 110%; ≥ 110%.

Duration of treatment will be presented by treatment group using a Kaplan-Meier curve whereby the last dose date will be the event date for those subjects who are off study therapy. Median duration of treatment and associated 95% CI will be provided. Subjects who are still on study therapy will be censored on their last dose date.

A by-subject listing of dosing of study medication (record of study medication, infusion details, and dose changes) and a listing of batch numbers will be also provided.

The key parameters used to calculate dosing data are shown below.

Table 7.4.1-1: Study Therapy Parameter Definitions

Monotherapy of Nivolumab		
Nivolumab		
Dosing schedule per protocol	3 mg/kg every 2 weeks	
Dose	Dose (mg/kg) is defined as Total Dose administered (mg)/Most recent weight (kg). Dose administered in mg at each dosing date and weight are collected on the CRF.	
Cumulative Dose	Cum dose (mg/kg) is sum of the doses (mg/kg) administered to a subject.	
Relative dose intensity (%)	Cum dose (mg/kg)/[(Last dose date - Start dose date + 14) x 3/14] x 100	
Duration of treatment	Last dose date - Start dose date +1	
Nivolumab combined with Ipilimumab		
	Nivolumab	Ipilimumab
Dosing Schedule per Protocol	3 mg/kg every 3 weeks for 4 doses followed by 3 mg/kg every 2 weeks	1 mg/kg every 3 weeks for 4 doses
Dose	Dose (mg/kg) is defined as Total Dose administered (mg)/Most recent weight (kg). Dose administered in mg at each dosing date and weight are collected on the CRF	Dose (mg/kg) is defined as Total Dose administered (mg)/Most recent weight (kg). Dose administered in mg at each dosing date and weight are collected on the CRF
Cumulative Dose	Cum Dose (mg/kg) is the sum of the doses administered to a subject.	Cum Dose (mg/kg) is the sum of the doses administered to a subject.
Cycle Duration _(i) (wk)	(Dose date _(i+1) - Dose date _(i))/7	N/A
Cycle Intensity _(i) (mg/kg/wk)	Dose _(i) /Cycle Duration _(i)	N/A
Relative Cycle Intensity _(i) (%)	(Cycle Intensity _(i) /intended dose per week) * 100	N/A
Relative Dose Intensity (%)	Sum of all Relative Cycle Intensities divided by N	Cum dose /[(Last dose date - Start dose date + 21) x 1/21] x 100
Duration of Treatment	Last dose date - Start dose date +1	Last dose date - Start dose date +1

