When study drugs (nivolumab and ipilimumab) are to be administered on the same day, nivolumab is to be administered first. Nivolumab infusion must be promptly followed by a normal saline or D5W flush to clear the line of nivolumab before starting the ipilimumab infusion. The second infusion will always be the ipilimumab study drug and will start after the infusion line has been flushed, filters changed and participant has been observed to ensure no infusion reaction has occurred. The time in between infusions is expected to be approximately 30 minutes but may be more or less depending on the situation.

Ipilimumab is to be administered as a 30 minute IV infusion, using a volumetric pump with a 0.2 to 1.2 micron in-line filter at the protocol-specified dose. The drug can be diluted with 0.9% normal saline or 5% Dextrose Injection to concentrations between 1 mg/mL and 4 mg/mL. It is not to be administered as an IV push or bolus injections. Care must be taken to assure sterility of the prepared solutions, since the drug product does not contain any antimicrobial preservatives or bacteriostatic agents. At the end of the infusion, flush the line with a sufficient quantity of normal saline or 5% dextrose solution.

The selection and timing of dose for each participant is as follows:

Table 7.1.2-1: Selection and Timing of Dose for Module B (Nivolumab and Ipilimumab Combination) - First 4 cycles

Study Treatment	Unit dose strength(s)/Dosage level(s)	Dosage formulation Frequency of Administration	Route of Administration
Nivolumab	3 mg/kg	Every 3 weeks	IV
Ipilimumab	1 mg/kg	Every 3 weeks	IV

Cycle 5 and beyond:

Participants should receive nivolumab at a dose of 3 mg/kg as a 30-minute IV infusion, on Day 1 of each treatment cycle every 2 weeks, starting 3 weeks after the fourth dose of the combination.

The selection and timing of dose for each participant is as follows:

Table 7.1.2-2: Selection and Timing of Dose for Module B (Nivolumab and Ipilimumab Combination) - Cycle 5 and Beyond

Study Treatment	Unit dose strength(s)/Dosage level(s)	Dosage formulation Frequency of Administration	Route of Administration
Nivolumab	3 mg/kg	Every 2 weeks	IV

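### Module B nivolumab dose intensity averages per-cycle ratios and gives the last dose no interval, so delayed courses can fall in the wrong category and the figure does not match Module A or ipilimumab

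*SAP*

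**What the plan says.** All three definitions stand in SAP Section 7.4.1, Table 7.4.1-1.

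- **Module A nivolumab:** "Cum dose (mg/kg)/[(Last dose date - Start dose date + 14) x 3/14] x 100". This is dose given over dose planned, and the last dose is credited with 14 days.
- **Module B ipilimumab:** "Cum dose /[(Last dose date - Start dose date + 21) x 1/21] x 100". The form is the same, and the last dose is credited with 21 days.
- **Module B nivolumab:** "Sum of all Relative Cycle Intensities divided by N". Each cycle's length in weeks is built from "Dose date _(i+1) - Dose date _(i))/7". The dose is divided by that length, and the result is expressed as a percentage of the intended weekly dose.

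The Module B nivolumab schedule in the table is "3 mg/kg every 3 weeks for 4 doses followed by 3 mg/kg every 2 weeks". Protocol Section 7.1.2 places the fifth dose 3 weeks after the fourth: "starting 3 weeks after the fourth dose of the combination".

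The table does not define N, gives no length for the last cycle, and has no rule for a child with one dose. SAP Section 7.4 applies the exposure analyses to all treated subjects. Section 7.4.1 reports relative dose intensity in categories cut at 50, 70, 90 and 110%.

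**The concern.** There are two separate problems. First, the text can be programmed in more than one way, and the answers differ most for children with few doses. Second, even once N is settled, a mean of ratios is not the ratio of totals. Each interval counts equally, however long it lasted, so a long gap gets less weight than the time it occupied.

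The same label then covers two different measures. The Module A and Module B nivolumab columns are not like for like, and nivolumab and ipilimumab can differ in one child treated with both on the same days. Dose intensity gives context for the safety results of each module, so a reader would naturally compare these columns.

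Short courses may be common. The historical median PFS used for Cohort 4 is 2.1 months, or 2.1 × 30.4375 = 64 days, which leaves room for three or four doses at 3-week intervals. The Cohort 2 figure is 2.25 months. These are control assumptions for two cohorts, not forecasts for the whole study.

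**Working it through.** The SAP states no numerical dose intensity, so there is no figure to reproduce. The check applies its formulas to chosen dose dates.

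**Inputs.** Every dose is 3 mg/kg of nivolumab (1 mg/kg of ipilimumab). The intended nivolumab rate is 3/3 = 1.0 mg/kg/week for the intervals after doses 1 to 4, and 3/2 = 1.5 mg/kg/week afterwards (SAP schedule and Protocol 7.1.2).

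**Readings of the Module B rule.**
- (a) N = doses given; the last dose adds nothing to the sum.
- (b) N = completed intervals.
- (c) The last dose is credited with its planned interval (100%); N = doses.

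**Benchmark.** The table's own cumulative form, extended to two phases: 100 × total dose ÷ sum of (interval × intended weekly rate), with the last interval at its planned length. In the 3-week phase this equals the ipilimumab formula when both drugs are given on the same dates.

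**On-time courses** (benchmark 100% throughout)

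| Doses | (a) | (b) | (c) |
|---|---|---|---|
| 1 | 0/1 = 0% | 0/0, undefined | 100% |
| 2 | 100/2 = 50% | 100% | 100% |
| 4 | 300/4 = 75% | 100% | 100% |
| 9 | 800/9 = 88.9% | 100% | 100% |
| 10 | 900/10 = 90.0% | 100% | 100% |

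Under (a), an on-time child reaches the 90 to <110% category only at the tenth dose.

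**Delayed courses.** In the 3-week phase, an 8-week interval has ratio (3/8)/1.0 = 37.5% and a 6-week interval 50%. In the 2-week phase, a 6-week interval has ratio (3/6)/1.5 = 33.3%.

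- *Two doses, gap 8.* (a) 37.5/2 = 18.8%; (b) 37.5%; (c) 137.5/2 = 68.8%. Benchmark 6/(8 + 3) = 54.5%. Ipilimumab 2/[(56 + 21)/21] = 54.5%. Readings (a) and (b) are in the wrong category.
- *Three doses, gaps 3 and 8.* (a) 137.5/3 = 45.8%; (b) 137.5/2 = 68.8%; (c) 237.5/3 = 79.2%. Benchmark 9/(3 + 8 + 3) = 64.3%. Ipilimumab 3/[(77 + 21)/21] = 64.3%. Readings (a) and (c) are in the wrong category.
- *Eight doses, gaps 3, 3, 3, 3, 2, 2, 6.* The ratios sum to 633.3. (a) 633.3/8 = 79.2%; (b) 633.3/7 = 90.5%; (c) 733.3/8 = 91.7%. Planned dose is 12 × 1.0 + (2 + 2 + 6 + 2) × 1.5 = 30 mg/kg, so the benchmark is 24/30 = 80.0%. Readings (b) and (c) are in the wrong category.
- *Two doses, gap 6.* (a) 25.0%; (b) 50.0%; (c) 75.0%. Benchmark 6/(6 + 3) = 66.7%. Readings (a) and (c) are in the wrong category.

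Every reading is misplaced in at least two of these four courses.

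**Same dates, two methods.** For four doses with gaps 2, 2 and 6 weeks, the Module A formula gives 12/[(70 + 14) × 3/14] = 12/18 = 66.7%. The averaging rule gives 233.3/3 = 77.8% under (b) and 333.3/4 = 83.3% under (c), one category higher.

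**How widespread.** All whole-week patterns with one or two delayed intervals were enumerated (up to 8 weeks after doses 1 to 4, up to 6 weeks later). The category differs from the benchmark under (a), (b), (c) in 5, 3 and 2 of 5 patterns at two doses; 34, 15 and 14 of 35 at three; and 133, 69 and 78 of 254 at six. These count patterns, not patients.

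**The case against.** **N has a natural meaning.** A sum of ratios divided by N reads as an ordinary mean, with N the number of ratios summed. A reader might infer from the 0%, 50% and 75% figures that every short course is misreported. The documents do not support that. On the natural reading, on-time courses are correct from two doses, and only one-dose children lack a value. This objection stands, and those figures are conditional on N counting doses.

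**The mean is a legitimate summary.** The intended rate changes after the 3-week phase, so the Module A formula could not be copied as it is, and the two-phase benchmark is not written in the SAP. That explains the choice but does not require averaging, because planned dose can be summed across phases. In the 3-week phase the benchmark is simply the ipilimumab formula in the same table.

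**Delays may be limited.** Protocol 8.1.2 sets 8 weeks from the previous dose during combination therapy, Protocol 8.1.1 sets 6 weeks for monotherapy, and SAP 7.4.2.1 gives 6 weeks for nivolumab without distinguishing. The SAP and Protocol statements need to be reconciled. The finding does not depend on which applies: the two examples with no gap above 6 weeks misplace (a) and (c), and (b) and (c), respectively. Longer gaps would show larger contrasts but need an exception.

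**Other tables show exposure.** Number of doses, cumulative dose, treatment duration, delays and by-subject listings are also reported. That stands, and it limits the harm.

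**A definition may exist elsewhere.** The table may have lost a footnote, and the Data Presentation Plan is not available. A definition of N would settle the one-dose and on-time cases, depending on its content, but not the averaging.

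**Conclusion.** The point holds, at minor importance. The visible rule leaves N and the last cycle undefined. Whichever reading is chosen, it can place delayed courses in a different category from the cumulative form used for the other two entries in the table. In the worked two- and three-dose examples with an 8-week gap, the error runs from 54.5 − 18.8 = 35.7 points too low to 79.2 − 64.3 = 14.9 points too high. In the eight-dose example, readings (b) and (c) are 10.5 and 11.7 points too high.

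Nivolumab dose intensity is therefore not comparable between modules, or with ipilimumab in the same child. This rests on full doses, on the planned rates listed above, and on taking the SAP's own cumulative form as the standard.

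A reader might also infer that the trial's conclusions are at risk. They are not: no efficacy test, futility rule or DLT decision uses dose intensity, and no formal comparison of the modules is specified. How many children would change category cannot be derived from the documents.

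**What to change.** Replace the Module B nivolumab entry in Table 7.4.1-1 with:

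100 × cumulative dose (mg/kg) ÷ planned dose (mg/kg) over the elapsed time,

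where planned dose accrues at the SAP's own rates: 3 mg/kg per 21 days for the intervals after doses 1 to 4, and 3 mg/kg per 14 days for later intervals. Set the last interval to its planned length (21 days if the last dose is among the first four, otherwise 14).

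Every on-schedule course, including a single dose, then gives 100%, as in Module A. The delayed examples become 54.5%, 64.3%, 80.0% and 66.7%. The per-cycle rows can be dropped or kept for listings.

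The cost is one formula and the matching program change. Dose dates, doses and weights are already collected. Version 2.0 of the SAP corrected the ipilimumab formula in this same section, so the change is of a kind already made.
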